9.2 Study Design Rationale

This is a phase II study to evaluate the efficacy and safety of two Therapeutic Doses (each dose 500 mCi, or 8 mCi/kg for subjects weighing 62.5 kg or less) of Ultratrace iobenguane I 131 in subjects with malignant pheochromocytoma or paraganglioma. Prior clinical studies have investigated the value of carrier-added iobenguane I 131 in treating malignant

pheochromocytoma or paraganglioma.³⁻¹⁸ Carrier–added iobenguane I 131 is approved for use in localization of pheochromocytoma and neuroblastoma.³⁶

Higher specific activity of iobenguane I 131 (i.e., Ultratrace iobenguane I 131) may result in greater tumor uptake of radioactivity. In animal studies, the Ultratrace form of iobenguane I 131 has shown increased uptake by normal tissue expressing norepinephrine transporter (NET) such as the heart. In xenografts, the Ultratrace form demonstrated higher radiopharmaceutical concentration in UVW/NET transfected tumors and in SK-N-BE (2c) neuroblastoma.

Subjects will receive baseline assessments including CT or MR and bone scan imaging. Subjects will be administered a 3 to 6 mCi Imaging Dose of Ultratrace iobenguane I 131 to confirm uptake of the study agent by at least one tumor. Each subject will then receive two Therapeutic Doses (each infusion 500 mCi, or 8 mCi/kg for subjects weighing 62.5 kg or less) of Ultratrace iobenguane I 131 at least three months apart. Within 7 days after each Therapeutic Dose, each subject will have a whole body scan. Pre-infusion safety measurements are to serve as the within-subject control for assessing post-infusion measurements for effects of Ultratrace iobenguane I 131 therapy.

As detailed in Section 9.1 Study Design, efficacy will be assessed through monitoring of use of concomitant medications, analyses of objective tumor response via CT or MR imaging, FDG scans (if available), and analysis of tumor marker levels. Safety will be assessed through analyses of treatment emergent adverse events (TEAEs), as well as baseline and pre- and post-infusion ECGs, physical examinations, vital signs measurements, laboratory measurements (including clinical chemistry, hematology and urinalysis), and human radiation absorbed dose estimates to target lesions and normal organs.

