9.5 Inclusion Criteria

To participate in this study, subjects must meet all of the inclusion criteria listed below.

All subjects must:

- 1. Provide written informed consent (and assent for subjects less than 18 years of age) and be willing to comply with protocol requirements
- 2. Be at least 12 years of age
- 3. Have a documented (medical record) diagnosis of either pheochromocytoma or paraganglioma that was confirmed by histology or a physician using other supportive data (e.g. abnormal MIBG diagnostic study, or elevated tumor markers).
- 4. Be ineligible for curative surgery for pheochromocytoma
- 5. Have failed a prior therapy for pheochromocytoma/paraganglioma or are not candidates for chemotherapy or other curative therapies
- 6. Be on stable antihypertensive medication regimen for tumor-related hypertension for at least 30 days prior to the first therapeutic dose. A stable antihypertensive medication regimen is defined as no addition or deletion of antihypertensive medication and no change in total daily dose or route of administration for currently used antihypertensive medication(s) in the 30 days prior to first therapeutic dose.
- 7. Have at least one tumor site by CT or MR or iobenguane I 131 scan
- 8. Have definitive MIBG tumor avidity
- 9. Have an expected survival period of at least 6 months as prognosticated by physician

Female subjects must:

- 10. Have a negative pregnancy test within 48 hours prior to receiving Ultratrace iobenguane I 131
- 11. Agree to use an acceptable form of birth control (abstinence, IUD, oral contraception, barrier and spermicide or hormonal implant) during this study and for 6 months following Therapeutic Doses of Ultratrace iobenguane I 131. For those women who are sexually active and using oral contraceptives, a second form of barrier contraception is required. or
- 12. Not be of childbearing potential as documented by history (e.g., tubal ligation or hysterectomy) or is post menopausal with a minimum of 1 year without menses

Male subjects must:

- Agree not to father a child during the period beginning immediately after administration of the first Therapeutic Dose of Ultratrace iobenguane I 131 during the study and ending six months after administration of the last Therapeutic Dose of Ultratrace iobenguane I 131.
- 14. Use an acceptable method of birth control (e.g., vasectomy or as described above) during the study and for six months following the Therapeutic Doses of Ultratrace iobenguane I 131.

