11.5.12 Changes in antihypertensive medication post Ultratrace iobenguane I 131 therapy

At each subject visit a current list of antihypertensive medication doses and compliance history will be obtained. Following Ultratrace iobenguane I 131 therapy, the potential for a decrease or normalization in the subject's pre-treatment hypertension exists.

For this situation, guidance on decreasing the dose of a specific antihypertensive medication, decreasing the number of different antihypertensive medication (e.g., two antihypertensive medications reduced to one), or total discontinuation of antihypertensive medication is as follows:

- A target blood pressure goal is systolic BP <140 mm Hg and diastolic BP as <90 mm Hg. If the subject's systolic and diastolic values are less than 140 mm Hg and less than 90 mm Hg respectively, a change in antihypertensive medication should be considered.
- Follow up blood pressure evaluations should be performed by health care professional in the manner described below within 7 to 10 days.
- The subject should measure and routinely record their blood pressure. Recordings should be at least 1-2 times/week at the same time of day [e.g., evening before supper or before bedtime] and preferably no more than 7 days between measurements. This provides a mechanism to recognize any potential increase in blood pressure after decreasing or discontinuing antihypertensive medications or, conversely, allows recognition of overmedication of antihypertensive medication. The subject will be instructed to communicate any blood pressure changes or questions to their physician.

If the subject remains within a normotensive range (systolic BP <140 mm Hg and diastolic BP as <90 mm Hg), consideration for further reduction or discontinuation of antihypertensive medication as noted above should be considered.

Presentation of tiredness, fatigue or orthostatic hypotensive signs or symptoms several weeks or more following a therapeutic dose of Ultratrace iobenguane I 131 could be an indication of excessive antihypertensive medication. In this situation, evaluation of blood pressure as noted above is suggested.

As an alternative, a 20-30 mm Hg drop of either systolic and/or diastolic blood pressure versus baseline, but still above the normotensive values noted above, may also represent an opportunity for antihypertensive medication dose decrease based upon clinical judgment.

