11.5.13 Vital Signs Measurements

Vital signs (blood pressure, pulse, temperature and respiration) will be collected at the time points listed below.

During Screening Period

Pre-dose: Within 4 hours prior to each administration of Ultratrace iobenguane I 131 (Imaging and Therapeutic)

Post-dose: Within 4 hours after each Ultratrace iobenguane I 131 administration

Both the professional staff (site staff or visiting nurse) and each subject will be obtaining blood pressure measurements for this study. The professional staff (site staff or visiting nurse) will measure heart rate and blood pressure using a manual mercury sphygmomanometer (or other device approved by MIP) at screening/baseline, twice weekly in the first 6 weeks following each therapeutic dose, weekly through Week 24 (at weeks when not collected twice weekly), and monthly at Months 7 through 12 as listed in the Schedule of Procedures (Appendix VII). If the second therapeutic dose is delayed, the twice weekly or weekly blood measurements may occur past Week 24. The twice weekly measurements will occur for at least 6 weeks after the second therapeutic dose and the weekly measurements will continue until at least 12 weeks past the second therapeutic dose. In addition, blood pressure and heart rate will be measured every time antihypertensive therapy is changed. If possible, the same site staff will measure the blood pressure for the subject's duration of the clinical trial. If it is not possible for the same personnel to measure the blood pressure for all determinations, care and accuracy of the blood pressure measurement will be emphasized.

The study subjects will be instructed to measure their blood pressure at least 1-2 times/week at the same time each day [e.g., evening before supper or before bedtime] and preferably no more than 7 days between measurements, from screening/baseline to the 12 month visit (Table 3). Subjects will be provided an Omron blood pressure monitor for blood pressure monitoring. Subjects will be trained by site staff to obtain their blood pressure measurements using the procedure outlined below.

TABLE 3: BLOOD PRESSURE MEASUREMENTS

(Blood pressure measurements should be obtained approximately the same time as baseline values throughout the study)	Screening /Baseline	First 6 weeks following therapeutic dose(s) (dose 1 and dose 2)	Through week 24 (at weeks when not collected twice weekly)	Months 7- 12

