7.4.2. Calculation of the Primary Endpoint

Criteria for Meeting the Primary Endpoint

Subjects must:

1. Receive an Imaging Dose
2. Receive at least one Therapeutic Dose
3. Have a reduction of each pre-therapeutic dosing (baseline) antihypertensive medication $\geq 50\%$ for a minimum of six consecutive months beginning during the 12-Month Efficacy Phase of the study, during which no new, long-term antihypertensive medication is introduced and maintained for longer than 14 days.

Considerations

1. The introduction of a new, transient (i.e., duration ≤ 14 days) antihypertensive medication regimen at any point during the study will not disqualify a subject from being able to achieve the primary efficacy endpoint. Short duration therapy may be instituted to address an acute increase in blood pressure that might be associated with a transient increase in catecholamine release secondary to a variety of factors including tumor cell death. On the contrary, the primary outcome measures chronic control of hypertension necessitated by long term catecholamine secretion by the active tumor.
2. A transient (i.e., duration ≤ 14 days) dose increase over the baseline dose of an existing antihypertensive medication regimen at any point during the study will not disqualify a subject from being able to achieve the primary endpoint. Existing antihypertensive therapy may be increased for a short duration to address an acute increase in blood pressure that might be

associated with a transient increase in catecholamine secretion secondary to a variety of factors including tumor cell death.

3. The introduction of a new, long-term (i.e., duration > 14 days) antihypertensive medication regimen after receiving a therapeutic dose will disqualify a subject from being able to achieve the primary endpoint while the subject is still taking any dose of the new medication. If the new long-term antihypertensive medication is discontinued, the start date for assessment of the primary endpoint is the date when both the new medication is discontinued and the baseline antihypertensive medications are reduced $\geq 50\%$.
4. New long-term antihypertensive medications introduced before Therapeutic Dose #1 is administered are considered part of the baseline antihypertensive medication regimen that must be reduced by at least 50% for achieving primary endpoint.

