7.5.10. Vital Signs Measurements

Vital signs (blood pressure, pulse, temperature and respiration) will be collected at the time points listed in the protocol. All vital signs measurements will be provided in listings. The listing will include all measurements recorded during the study, with a column included for origin (e.g., health care provider vs. subject measurement).

Summary statistics of vital signs and the changes from Screening will be presented in the table by visit according to its respective visit window. Pre-dose to post-dose changes for each administration of iobenguane I 131 will also be summarized.

Heart rate and blood pressure measurements are recorded both by healthcare providers and by the subjects, as indicated in the protocol. The results from the healthcare providers at site visits or at the subjects' homes will be combined for each subject for sitting and supine positions and respective visit window as indicated in [Appendix 1](#). This table will exclude blood pressure readings by subjects themselves. The recordings done by the subjects themselves were used to help guide the investigators in management of anti-hypertensive medications, but were not intended to be included in the vital sign data set. The mean values for each subject and time point will be used as the basis of the summaries. Summary statistics for heart rate and blood pressure results and their respective changes from baseline will be prepared.

Subjects who develop changes from Screening or values of potential clinical importance will be tabulated by study visit and overall, and will be flagged in the subject data listings. Criteria will be as follows:

- Systolic BP increase or decrease >20 mmHg
- Diastolic BP increase or decrease >10 mmHg
- Pulse rate increase or decrease >20 bpm
- Temperature >38.0°C or >100.4°F

Vital signs obtained within 24 hours of administration of the study drug will also be flagged if the change in BP or pulse rate specified above occurred compared to the vital signs obtained 30 minutes pre-administration.

By-subject figures for systolic and diastolic BP measurements for sitting and supine positions combined relative to days post first therapeutic infusion, along with antihypertensive medication dose, will be provided as indicated in [Section 7.4.2](#). Two set of figures will be provided: one set will exclude measurements obtained by the subject. The other set will present the measurements obtained by the subjects.

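### Blood pressure change is referenced to Screening, up to 58 days before dose 1, but medication change to the dose-1 regimen, so tabulated BP changes can include a pre-treatment change in either direction

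*Protocol*

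**What the plan says.** **BP reference.** SAP 7.5.10 states: "Summary statistics of vital signs and the changes from Screening will be presented in the table by visit according to its respective visit window". The flags follow the same rule: "Subjects who develop changes from Screening or values of potential clinical importance will be tabulated by study visit and overall", with thresholds of more than 20 mmHg systolic and more than 10 mmHg diastolic. For the healthcare-provider heart-rate and BP summary, the section speaks of change from baseline and does not say which reading that is. In SAP Appendix 1 the only BP window labelled baseline is Day -28 to Day 0, counted from the Imaging Dose. The protocol's Schedule of Procedures also places screening in the four weeks before imaging.

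**Time from imaging to treatment.** Protocol 10.1 and 10.7 allow up to 30 days between the Imaging Dose and Therapeutic Dose 1.

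**Medication reference.** SAP 7.4.1 uses the daily dose being taken on the day of Therapeutic Dose 1. SAP 7.4.2, Consideration 4, adds: "New long-term antihypertensive medications introduced before Therapeutic Dose #1 is administered are considered part of the baseline antihypertensive medication regimen". Protocol 9.5, Inclusion 6, requires "no change in total daily dose or route of administration for currently used antihypertensive medication(s) in the 30 days prior to first therapeutic dose".

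**Readings close to dosing.** Protocol 11.5.13 schedules vital signs "Within 4 hours prior to each administration of Ultratrace iobenguane I 131 (Imaging and Therapeutic". Protocol 9.2 says: "Pre-infusion safety measurements are to serve as the within-subject control for assessing post-infusion measurements". SAP 7.1 and Appendix 1 give the reading before dose 1 its own summary window, and SAP 7.5.10 also uses it for the change around each infusion.

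**Role of BP.** The Study Outline lists hypertension status and BP change among the secondary endpoints.

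**The concern.** BP and antihypertensive use are two sides of one clinical question, and a reader will set them side by side. If the BP reference was read on one regimen and the medication reference is another, the two changes do not describe the same period. A BP shift produced by a drug started or stopped before treatment would appear in the tables as a change after treatment.

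The trial has a single arm, so no control group separates a pre-treatment shift from an effect of study drug. SAP 7.4 has no separate tabulated analysis of BP change, so the tables in 7.5.10 are where this secondary endpoint will be read. The individual flags inherit the same reference.

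**Working it through.** The plan states no figure for this interval, so there is none to reproduce. The check is arithmetic on the windows.

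**Inputs**
- Screening window: 28 days before the Imaging Dose (SAP Appendix 1; Protocol Appendix VII).
- Imaging Dose to Therapeutic Dose 1: at most 30 days (Protocol 10.1, 10.7).
- Required stability of the regimen: 30 days before dose 1 (Protocol 9.5).

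**Step 1. Longest lag from Screening BP to dose 1.** 28 + 30 = 58 days. Under the SAP 7.1 day formula, which adds 1, Day -28 is 29 days before imaging, and the limit becomes 29 + 30 = 59 days.

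**Step 2. Part of the lag not covered by the stability rule.** max(0, lag - 30) = 58 - 30 = 28 days (29 under the SAP formula).

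**Step 3. Dependence on the imaging gap.** The gap varies by subject and its distribution is not given, so a range is shown:

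| Imaging to dose 1 (days, assumed) | Longest lag (gap + 28) | Longest uncovered interval (lag - 30) |
|---|---|---|
| 2 | 30 | 0 |
| 5 | 33 | 3 |
| 7 | 35 | 5 |
| 14 | 42 | 12 |
| 21 | 49 | 19 |
| 30 | 58 | 28 |

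**Step 4. What enters the tabulated change.** For any subject and visit:

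BP(visit) - BP(Screening) = [BP(dose 1) - BP(Screening)] + [BP(visit) - BP(dose 1)]

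Only the second bracket follows treatment. The first is the error in that subject's tabulated change, and it can push a subject over or under a flag threshold.

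**Step 5. Direction of the first bracket.**
- A long-term drug added after the Screening reading and before dose 1 belongs to the medication baseline under Consideration 4. Its BP effect would exaggerate a later fall.
- Protocol 11.5.3 requires labetalol to be stopped before dose 1, and Appendix III drugs to be off for five half-lives before imaging. Labetalol and reserpine are on both the excluded list (Appendix III) and the list of antihypertensives (Appendix V). Withdrawal would tend to raise BP before dose 1 and so mask a later fall.
- The labetalol text can be read as allowing the stop inside the last 30 days, which does not fit Inclusion 6. Those passages must be reconciled. On that reading, a mismatch can arise even when the lag is under 30 days.

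**Step 6. After the change proposed below.** The dose-day reading is at most 4 hours before dose 1. Every other reading in the average is on the same regimen and within 30 days. The uncovered interval falls from at most 28 days to 0.

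**The case against.** The case against has several good parts.

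- **The shift may be visible.** The reading before dose 1 is its own window, so the by-visit table should show any group shift between Screening and dose 1. The by-subject figures plot BP with drug dose over time, and a listing pairs them. This stands: the displays may reveal the problem. They do not correct the later changes from Screening or the flags.
- **Extra readings may dilute it.** Protocol 11.5.13 asks for a provider BP whenever antihypertensive therapy changes. A change that respects Inclusion 6 falls at least 30 days before dose 1, hence on or before imaging and inside the Screening window. SAP 7.5.10 averages provider readings within a window, so a reading on the new regimen can enter the Screening mean. This stands in part, but the mean then mixes two regimens.
- **Protocol 9.2 is not contradicted.** A Screening reading is also taken before infusion. This stands: 9.2 favours a reading close to dosing but does not specify the one within 4 hours.
- **Consequences are limited.** No test or success rule is attached to BP change. This stands.

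A reader might also infer more than the documents support:

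- **That the bias always favours the drug.** The withdrawals in Protocol 11.5.3 work the other way, and Consideration 4 is a handling rule, not a forecast that drugs will be added.
- **That every BP summary uses Screening.** That is explicit for the general vital-signs table and the flags. For the provider summary it is inferred from a window label.
- **That the bias can be sized.** If both intervals are uniform, P(lag > 30) = 14/30 = 47%. With an imaging gap uniform over 2 to 14 days (assumed), it is 6/28 = 21%. Either figure is the share of old readings, not the share of changed regimens. Assuming a 5 to 15 mmHg effect in 10 to 20% of subjects would give 0.10 × 5 = 0.5 to 0.20 × 15 = 3 mmHg in the mean, but nothing in the documents supports those inputs.

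**Conclusion.** The point holds as a defect in how BP change is referenced. By-visit vital-sign changes and the BP flags start from a reading that can be 58 days before dose 1. The medication baseline is the dose-1 regimen, with stability required for 30 days. The provider summary leaves its baseline undefined. In subjects whose antihypertensives changed between the two dates, a pre-treatment change can be reported as post-treatment, in either direction.

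The 58 days is a limit that follows from the stated windows, not a typical value. The number of subjects affected and the size of the bias are unknown.

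A reader might infer that the response rate is inflated. It is not: SAP 7.4.1 and 7.4.2 calculate the primary endpoint from medication alone. The effect is confined to the secondary BP endpoint and the vital-sign flags. The change is worth making because the readings are already scheduled.

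**What to change.** In SAP 7.5.10 and Appendix 1, define one BP and heart-rate baseline for all post-therapy change summaries and flags: the mean of provider readings taken on the dose-1 regimen before Therapeutic Dose 1. It comprises the reading within 4 hours before dose 1 and any other provider readings taken after the last regimen change and within the 30 days before dose 1. Keep change from Screening as a supporting display.

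**Cost.** SAP wording and a second set of change columns; no new data. A dose-day reading may be raised by the setting, which would make later falls look larger where nothing else is available to average. The pre-imaging reading falls within the 30 days, so a second reading should usually exist if the regimen was unchanged since imaging.

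Protocol 11.5.12 refers to "a 20-30 mm Hg drop of either systolic and/or diastolic blood pressure versus baseline" without defining baseline. That text guides medication decisions, so the request is only that the term be defined and the passages reconciled. No reference is proposed here.

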Endpoints:	 Primary Endpoint: The primary endpoint for this trial is the proportion of study subjects with a reduction (including discontinuation) of all antihypertensive medication by at least 50% for at least six months or two cycles Ultratrace iobenguane I 131. The primary endpoint will be assessed at the time of study completion or discontinuation, whichever occurs first. Secondary Endpoints: Proportion of subjects with overall tumor response of CR or PR per RECIST criteria, Proportion of subjects with overall tumor response of CR, PR or MR (moderate response) per RECIST criteria Bone lesion response per the Soloway Scale Tumor marker response in 24 hr urine and other serum/plasma tumor markers associated with pheochromocytoma/paraganglioma Status of hypertension and changes in blood pressure Quality of Life per the recommended guidelines from the EORTC
	 QLQ-C30 manual Symptoms as evaluated through the NIH Quality of Life and Symptoms Questionnaire for Pheochromocytoma and Paraganglioma
	Change in use of analgesics and pain medications
	• Overall survival (OS), defined as the time from the date of enrollment to the date of death from any cause. OS time will be censored at the last date the subject is known to be alive when the confirmation is absent or unknown.
	 Safety assessed by changes in lab values, physical exams or vital signs, and the occurrence of treatment emergent adverse events Human radiation absorbed dose estimates to normal organs
Sample Size:	It is anticipated that approximately 75 subjects will be enrolled to ensure that 58 subjects receive two doses and are evaluable for safety and efficacy. The one-sided alternative hypothesis of the study is that the proportion of subjects experiencing a reduction (including discontinuation) of all antihypertensive medication by at least 50% for at least six months or two cycles is 0.25, against the null hypothesis that the proportion is 0.10. Sample size of 58 subjects in the Per Protocol Set was based on a one-sided significance level of $\alpha = 0.025$ and power of 0.90 (90%).
Statistical Methods:	Summary tables and listings of demographics and baseline characteristics for all enrolled subjects will be presented. Listings of laboratory test results collected at baseline and during the study will be generated.

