Site staff or visiting nurse ^a (blood pressure and heart rate)	Х	2X a week ^b	1X a week ^b	1X a month
Subject	From screening/baseline through 12 month visit at least 1-2X per week (no more than 7 days between measurements)			

^a Blood pressure and heart rate will be measured every time antihypertensive therapy is changed

^b If the second therapeutic dose is delayed ,the twice weekly or weekly blood measurements may occur past 24 weeks. The twice weekly measurements will occur for at least 6 weeks after the second therapeutic dose and weekly measurements will continue until at least 12 weeks past the second therapeutic dose

Prior to obtaining the blood pressure measurements, the subjects should sit quietly after resting for 5 minutes, with the arm supported on a flat surface, such that the upper arm is supported at the level of the heart. The subject's back should be supported, and both feet should be flat on the floor. An appropriately sized cuff should be placed on the subject's non-dominant arm. Within thirty minutes prior to the blood pressure measurement, subjects should refrain from smoking, drinking coffee or other caffeinated beverage, or exercising. At least two, and preferably three, readings should be taken at each sitting with at least a one minute interval between readings. A summary of recommendations for Home Blood Pressure Monitoring will be included as part of the Study Manual Binder.

If a subject develops symptoms consistent with orthostatic hypotension (light headedness, dizziness or changes in sensorium upon standing) at any point, his or her supine and standing blood pressure and heart rate should be collected. An evaluation of orthostatic hypotension should be performed to determine if the cause could be from excessive antihypertensive medication versus some other clinical explanation (e.g., dehydration). Whenever possible, blood pressure measurements should be obtained at approximately the same time as baseline values (e.g., morning).

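### SAP 7.5.10 averages supine with sitting blood pressure although the protocol standardises on seated readings, and no planned table or figure shows the supine-to-standing change

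*Protocol*

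**What the plan says.** **Protocol.** Section 11.5.13 sets out one technique for blood pressure: "the subjects should sit quietly after resting for 5 minutes, with the arm supported on a flat surface", with back support and both feet on the floor. On repetition it says: "At least two, and preferably three, readings should be taken at each sitting with at least a one minute interval between readings". The only instruction for other positions is conditional: "If a subject develops symptoms consistent with orthostatic hypotension (light headedness, dizziness or changes in sensorium upon standing) at any point", then "his or her supine and standing blood pressure and heart rate should be collected". The stated purpose is to judge whether excessive antihypertensive medication or another cause, such as dehydration, explains the symptoms. Section 11.5.12 makes the same link, naming "orthostatic hypotensive signs or symptoms several weeks or more following a therapeutic dose" as a possible sign of over-medication. The secondary endpoints in the Study Outline include "Status of hypertension and changes in blood pressure".

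**SAP.** Section 7.5.10 says that provider results "will be combined for each subject for sitting and supine positions and respective visit window", and that the mean per subject and time point is the basis of the summaries. It repeats the pooling for the graphs: "By-subject figures for systolic and diastolic BP measurements for sitting and supine positions combined", plotted with antihypertensive dose. Section 7.4.1 also calls for the mean provider blood pressure per visit window in the medication figures. The SAP nowhere mentions standing readings. Its blood-pressure flags (systolic change >20 mmHg, diastolic change >10 mmHg) compare with Screening, or with pre-administration values for readings within 24 hours of dosing. Section 11 lists two vital-signs change tables, 14.3.5.1.1 and 14.3.5.1.2; neither is orthostatic by title or description. All vital signs are listed, but the only added column that 7.5.10 names is the origin of the reading.

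**The concern.** Under the protocol's own instruction, a supine reading is taken to be compared with a standing one, and it is triggered by symptoms. Averaging it with seated readings changes what the window mean measures, and does so in the windows where over-medication is being considered. If the baseline is seated, part of an apparent change can be posture.

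The contrast that the supine and standing pair was taken to show, the postural change in blood pressure and heart rate, is not summarised. This matters because the primary endpoint is a reduction in antihypertensive medication. The by-subject figures are where a reader would check whether blood pressure stayed controlled as doses changed, and orthostatic findings bear on why a dose was changed.

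**Working it through.** The documents give no figure to reproduce, so the check compares the passages and then works an illustration on stated assumptions.

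**1. Positions collected and positions summarised**

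- Sitting: the routine position in protocol 11.5.13. It is in the SAP window means and the by-subject figures.
- Supine: requested only with orthostatic symptoms. It is averaged with sitting in the same means and figures.
- Standing: requested only with orthostatic symptoms. It is not named in the SAP rule for means or figures.
- Supine minus standing: the contrast the protocol asks for. It is in no planned table or figure.

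**2. Shift in a subject's window mean**

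Let d be the supine-minus-sitting difference, with every reading weighted equally:

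shift = d × n_supine / (n_sitting + n_supine)

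Neither d nor the number of supine readings is in the documents; both are assumed. The number of sitting readings per session (2 to 3) is from protocol 11.5.13.

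- Equal numbers of each: the supine share is 1/2, so d = 0 to 10 mmHg gives a shift of 0 to 5 mmHg.
- One session (2 to 3 sitting readings) with 1 to 3 supine readings: the share runs from 1/(3+1) = 25% to 3/(2+3) = 60%.
- Twice-weekly window (2 sessions, so 4 to 6 sitting readings) with 1 to 3 supine readings: the share runs from 1/(6+1) = 14% to 3/(4+3) = 43%.
- Across both cases, each 10 mmHg of d moves the window mean by 10 × 0.14 = 1.4 to 10 × 0.60 = 6 mmHg. The direction follows the sign of d.

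**3. A worked window (all values assumed)**

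Take two sitting readings averaging 120 mmHg, two supine averaging 130 and two standing averaging 105. The SAP value is (120 + 120 + 130 + 130)/4 = 125, which is 5 mmHg above the seated mean. The postural fall is 130 − 105 = 25 mmHg, and no planned table or figure shows it.

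**4. Group level**

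If 5% of subjects in a window were affected (assumed) and each shifted by 5 mmHg, the group mean would move by 0.05 × 5 = 0.25 mmHg.

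**5. The competing window rule**

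SAP Appendix 1 says that the assessment closest to nominal time is used, which does not agree with the mean in 7.5.10. Following Appendix 1 would not remove the problem: a single supine reading could then represent the window, and the shift for that subject would be the whole of d.

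**The case against.** The other side has several good points.

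- **Supine readings may have other sources.** Protocol 11.5.13 also requires vital signs within 4 hours before and after every administration, and that list states no position. The seated instruction may cover those readings, but supine ones around dosing or imaging are not excluded. A reader might infer that every pooled supine value is half of an orthostatic pair; the documents do not show this.
- **Standing values are not wholly lost.** A reader might infer that they can appear only in listings. The tabulation of changes from Screening in SAP 7.5.10 has no position restriction, so a low standing value could be counted in Table 14.3.5.1.2. Standing values are left out of the means because they are not named, not by an explicit rule, and keeping them out of a resting mean is reasonable.
- **The harm can be reported elsewhere.** Protocol 12.5 has worsening vital signs assessed as possible adverse events, and treatment-emergent events are tabulated. The NIH questionnaire asks about decreased blood pressure and dizziness and is summarised by item. It would be wrong to say that orthostatic hypotension is never summarised.
- **The endpoint is descriptive.** Blood-pressure change is in the protocol's endpoint list but not among the objectives in protocol section 8 or SAP 4.3, and no test or success rule depends on it.
- **Symptom-triggered readings have no systematic denominator**, so listing them is defensible.

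All of this limits the point but does not remove it. Whatever the source of the supine readings, averaging them with seated ones mixes positions. The adverse-event tables do not show the measured fall, and the named listing columns do not include position, so a reader may be unable to reconstruct it.

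**Conclusion.** The point holds in a limited form. The SAP states a pooling rule that departs from the protocol's seated standard, and the supine-to-standing change has no planned table or figure.

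The effect is confined to windows with supine readings. On the assumptions shown (d of 0 to 10 mmHg, equal numbers of readings, equal weights) it is 0 to 5 mmHg in one subject's window mean. The documents do not say how often this would occur. A reader might infer that the blood-pressure results as a whole track position rather than treatment; nothing in the documents supports that, and the group-level illustration is a fraction of 1 mmHg. The primary endpoint rests on medication dose and duration and is untouched.

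The change is worth making because it is cheap and because the by-subject figures are read alongside the medication data.

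**What to change.** In SAP 7.5.10:

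1. Base the by-window blood-pressure and heart-rate means, their changes and the by-subject figures on sitting readings. Use a supine value only where a window has no sitting reading, and flag it. Align the wording with 7.4.1 and Appendix 1 so that one rule (mean or closest assessment) applies.
2. Add position as a column in the vital-signs listing.
3. Add one descriptive table of subjects with a symptom-triggered orthostatic evaluation. It should give the supine-to-standing change in blood pressure and heart rate, the time from each Therapeutic Dose and the antihypertensive status at that date. Count falls above a pre-specified reporting threshold. The SAP's >20/>10 mmHg values could be reused as a descriptive cut-off, with a note that in the SAP they are change-from-Screening flags and not orthostatic criteria.
4. State that these readings are symptom-triggered and have no systematic denominator.

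The cost is SAP wording, one listing column and one small table. No new data are requested and no clinical rule changes. There are two downsides. Some windows will rest on fewer readings, and a few may still carry a flagged supine value. The table also depends on position and time having been recorded well enough to pair readings: the SAP's reference to positions suggests that position was captured, but the case report form is not in the documents, so this should be confirmed first.
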